## 10. Thrombosis

## 11. Bleeding complications requiring intervention or transfusion of blood.

Please refer to Appendix A for definitions of stroke/TIA and classification of bleeding events. Each adverse event will be evaluated by the investigator for relatedness and seriousness.

The communication requirements for reporting to BSC are as shown in Table 6:

**Table 6: Investigator Reporting Requirements**

Event Classification	Communication Method	Communication Timeline
Unanticipated Serious Adverse Device Effect	Complete AE eCRF page with all available new and updated information	
 
○ Within 1 business day of first becoming aware of the event.
 
○ Terminating at the end of the study
 

Serious Adverse Event including Serious Adverse Device Effects	Complete AE eCRF page with all available new and updated information	
 
○ Within 2 business days of first becoming aware of the event or as per local/regional regulations.
 
○ Reporting required through the end of the study
 

	Provide all relevant source documentation (unidentified) for reported event	
 
○ When documentation is available
 

Adverse Event	Complete AE eCRF page, which contains such information as date of AE, treatment of AE resolution, assessment of seriousness and relationship to the device	
 
○ No later than 14 working days after becoming aware of the information
 
○ Reporting required through the last visit of the patient in the study, with the exception of following up open adverse events until resolved or considered stable.
 

Device Deficiencies (including but not limited to failures, malfunctions, and product nonconformities) Note: Any Investigational Device Deficiency that might have led to a serious adverse event if a) suitable action had not been taken or b) intervention had not been made or c) if circumstances had been	Complete applicable Device Deficiency CRF page with all available new and updated information	
 
○ Investigators should report within 14 business days of first becoming aware of the event and as per local/regional regulations
 
○ Reporting required through the end of the study
 

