### 16.2. *Investigator Responsibilities*

The Principal Investigator of an investigational center is responsible for ensuring that the study is conducted in accordance with the Clinical Study Agreement, the investigational plan/protocol, ISO 14155, ethical principles that have their origins in the Declaration of Helsinki, any conditions of approval imposed by the reviewing IRB/EC, and prevailing local and/or country laws and/or regulations, whichever affords the greater protection to the subject.

The Principal Investigator's responsibilities include, but are not limited to, the following.

- Prior to beginning the study, sign the Investigator Agreement and Protocol Signature page documenting his/her agreement to conduct the study in accordance with the protocol.
- Provide his/her qualifications and experience to assume responsibility for the proper conduct of the study and that of key members of the center team through up-to-date curriculum vitae or other relevant documentation and disclose potential conflicts of interest, including financial, that may interfere with the conduct of the clinical study or interpretation of results.
- Make no changes in or deviate from this protocol, except to protect the life and physical well-being of a subject in an emergency; document and explain any deviation from the approved protocol that occurred during the course of the clinical investigation.
- Create and maintain source documents throughout the clinical study and ensure their availability with direct access during monitoring visits or audits; ensure that all clinical-investigation-related records are retained per requirements.
- Ensure the accuracy, completeness, legibility, and timeliness of the data reported to the sponsor in the CRFs and in all required reports.
- Record, report, and assess (seriousness and relationship to the device/procedure) every adverse event and observed device deficiency.
- Report to BSC, per the protocol requirements, all SAEs and device deficiencies that could have led to a SADE.
- Report to the IRB/EC and regulatory authorities any SAEs and device deficiencies that could have led to a SADE, if required by the national regulations or this protocol or by the IRB/EC, and supply BSC with any additional requested information related to the safety reporting of a particular event.
- Allow the sponsor to perform monitoring and auditing activities, and be accessible to the monitor and respond to questions during monitoring visits.

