**Table 6: Investigator Reporting Requirements**

Event Classification	Communication Method	Communication Timeline
less fortunate is considered a reportable event.		

Abbreviations: AE=adverse event; CRF=case report form; IDE=Investigational Device Exemption; UADE=unanticipated adverse device effect

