### ***20.2. Boston Scientific Device Deficiencies***

All device deficiencies will be documented and reported to BSC on the appropriate eCRF within 14 business days of first becoming aware of the event. Device deficiencies are not to be reported as adverse events. However, if there is an adverse event that results from a device deficiency, that specific event would be recorded on the appropriate eCRF. If possible, the device(s) should be returned to BSC for analysis. If it is not possible to return the device, the investigator should document why the device was not returned and the final disposition of the device. Device deficiencies should also be documented in the subject's medical record.

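### Device deficiencies are not graded by seriousness: one that might have led to an SAE has a reporting deadline 12 business days longer than an SAE's

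*Combined protocol and SAP*

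**What the plan says.** Table 6 (Investigator Reporting Requirements) sets the time a site has to report to the sponsor. A USADE is due "Within 1 business day of first becoming aware of the event". An SAE, including a SADE, is due "Within 2 business days of first becoming aware of the event or as per local/regional regulations". Other adverse events have 14 working days. Device deficiencies have a single row: "Investigators should report within 14 business days of first becoming aware of the event and as per local/regional regulations".

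That row carries a Note on a subset. It begins "Any Investigational Device Deficiency that might have led to a serious adverse event if a) suitable action had not been taken", adds the cases where no intervention had been made or luck had been worse, and ends "less fortunate is considered a reportable event". It gives the subset no deadline of its own.

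Section 20.2 repeats the single limit: "All device deficiencies will be documented and reported to BSC on the appropriate eCRF within 14 business days of first becoming aware of the event". It adds that deficiencies are not to be entered as adverse events, although an adverse event that results from one is recorded separately.

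Section 16.2 lists among the investigator's duties: "Report to BSC, per the protocol requirements, all SAEs and device deficiencies that could have led to a SADE". The next duty in that list pairs the same two classes for reports to the ethics committee and authorities, where required.

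**The concern.** The protocol identifies potentially serious deficiencies twice, in the Table 6 Note and in 16.2, and then gives them the same deadline as a trivial deficiency. A device malfunction that is corrected before anyone is hurt can carry the same information about the next implant as one that injures. Under Table 6 the second is due in 1 or 2 business days and the first in 14.

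What is at stake is the speed of a safety signal. Section 18.2 lists device embolization and inability to move or retrieve the device among the possible events, and a deficiency without harm may be an early sign of either. Section 21.1 gives safety oversight to the sponsor's Medical Safety group, and 20.3 makes the sponsor responsible for passing adverse event information to the other investigators. Enrolment meanwhile continues at up to 70 sites (8.1).

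**Working it through.** **Step 1. The deadlines side by side.**

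| Class | Time to report to the sponsor | Source |
|---|---|---|
| USADE | 1 business day | Table 6 |
| SAE, including SADE | 2 business days, or per local rules | Table 6 |
| Other adverse event | 14 working days | Table 6 |
| Any device deficiency | 14 business days, and per local rules | Table 6 |
| Any device deficiency | 14 business days | 20.2 |
| Deficiency that might have led to an SAE | none of its own; sits in the 14-business-day row | Table 6, Note |

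Table 6 and 20.2 agree. Adverse events are graded by seriousness; deficiencies are not.

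**Step 2. Does 16.2 set a shorter time?** No. It joins SAEs and potentially serious deficiencies in one duty, but leaves the manner and time to the protocol's requirements. That leads back to Table 6 and 20.2, where 2 business days is written for SAEs only.

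**Step 3. Is there a faster route for a potentially serious deficiency?** There are three cases.
- It caused a serious adverse event. That event is recorded in its own right (20.2) and takes the 1- or 2-business-day row. The SAE definition in Table 5 includes serious deterioration that led to an intervention to prevent life-threatening or permanent harm, so some rescued failures belong here.
- It caused only a non-serious adverse event. The event has 14 working days and the deficiency 14 business days.
- It caused no adverse event. Section 20.2 keeps it off the adverse event form, so only the 14-business-day row applies.

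In the last two cases the only thing that can shorten the time is the clause on local rules, which depends on the country.

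**Step 4. Size of the difference.** Deadlines: 14 − 2 = 12 business days. Counting from each weekday and ignoring holidays, 14 business days span 18 to 20 calendar days and 2 span 2 to 4. The gap for a given starting day is 16 to 18 calendar days.

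**Step 5. Registry procedures in that gap.** Inputs: about 1000 subjects and 21 months (8.1). A subject counts as enrolled only once the implant procedure has started (10.1), so enrolments stand in for procedures. Assumptions: even enrolment and 21.7 business days a month.
- Pace: 1000 / (21 × 21.7) = 2.19 per business day.
- In 14 business days: 2.19 × 14 = 30.7. In 2 business days: 2.19 × 2 = 4.4.
- Difference: 30.7 − 4.4 = 26.3, about 26.

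Check in calendar days: 1000 / (21 × 365.25 / 12) = 1.56 per day. Unrounded, this gives 25.0 over 16 days and 28.2 over 18 days. The two counts agree.

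**The case against.** The strongest reply is that nothing here is inconsistent. A reader might infer from 16.2 that the protocol puts these deficiencies on the SAE deadline and that Table 6 then contradicts it. The documents do not support that: 16.2 pairs the duty and defers on timing, and the two places that state a time agree. This stands, and the point is one of design.

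The gap is also narrower than it first appears. Deficiencies that led to a serious adverse event are already on the fast rows. Embolization and failure to retrieve are listed in 18.2 as adverse events or device effects, so if they occur and are serious they are not delayed. The deficiency row joins its local-rules clause with *and*, so a shorter local rule binds in addition to the 14 business days. All of this stands. It leaves the deficiency with no adverse event, or only a non-serious one, in countries without a shorter rule.

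A reader might also take 31 procedures as the number of patients exposed to an undisclosed hazard. That is not supported. It is a gross count, of which about 4 would occur under the 2-day limit too. It assumes the full allowance is used, and the documents give no deficiency rate.

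Finally, this is an observational study of a CE-marked device (sections 4 and 8.2), with on-site and remote monitoring (17, 21.1). The sponsor may hear of a deficiency by another path, so one cannot say that it could not act before the site's report arrives. But the documents describe no faster protocol-wide route, and the deadline that sites are given is 14 business days.

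**Conclusion.** The point holds as a gap in grading. Table 6 and 20.2 consistently allow 14 business days for every device deficiency, including the subset that the Table 6 Note marks out. A deficiency in that subset that caused no serious adverse event may reach the sponsor up to 12 business days later than an SAE would, unless a local rule is shorter. It would go too far to say that such reports will be late: 14 business days is a maximum, and sites may report sooner.

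About 26 further registry procedures (25 to 28 on the calendar count) could take place in that interval. The figure rests on even enrolment, on 21.7 business days a month, and on use of the full allowance. It is a ceiling at the average planned pace and says nothing about the probability of harm. Implants outside the registry are not counted.

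The primary analyses, the precision figures in Table 3 and the sample size are untouched. The change is worth making because it is cheap and uses a class and a timeline that the protocol already defines.

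**What to change.** Split the device-deficiency row of Table 6, and the first sentence of 20.2, in two:

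- Deficiencies meeting the Table 6 Note follow the existing SAE reporting timeline: 2 business days, or sooner where local rules require.
- All other deficiencies stay at 14 business days.

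Section 16.2 can stay as it is, since its reference to the protocol's requirements would then lead to a graded rule.

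The cost is one table row and one sentence. Sites report a small subset of deficiencies sooner, on the existing form, and must judge on learning of a deficiency whether it meets the Note. No visits, procedures or analyses are added.

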**Table 6: Investigator Reporting Requirements**

Event Classification	Communication Method	Communication Timeline
less fortunate is considered a reportable event.		

Abbreviations: AE=adverse event; CRF=case report form; IDE=Investigational Device Exemption; UADE=unanticipated adverse device effect

### ***20.2. Boston Scientific Device Deficiencies***

All device deficiencies will be documented and reported to BSC on the appropriate eCRF within 14 business days of first becoming aware of the event. Device deficiencies are not to be reported as adverse events. However, if there is an adverse event that results from a device deficiency, that specific event would be recorded on the appropriate eCRF. If possible, the device(s) should be returned to BSC for analysis. If it is not possible to return the device, the investigator should document why the device was not returned and the final disposition of the device. Device deficiencies should also be documented in the subject's medical record.

### ***20.3. Reporting to Regulatory Authorities / IRBs / ECs / Investigators***

BSC is responsible for reporting adverse event information to all participating investigators and regulatory authorities, as applicable. The Principal Investigator is responsible for informing the IRB/EC, and regulatory authorities of UADE and SAE as per local/regional requirements.

## **21. Committees**

### ***21.1. Safety Monitoring Process***

The BSC Medical Safety group will provide safety oversight and classify individual events. During regularly scheduled monitoring visits, clinical research monitors will support the dynamic reporting process through their review of source document information.

The BSC Medical Safety group includes physicians with expertise in Electrophysiology (EP), and/ or Cardiology, as well as other healthcare professionals with the necessary therapeutic and subject matter expertise to evaluate and classify the events into the categories outlined above

### ***21.2. Executive/Steering Committee***

An Executive Committee composed of the sponsor's Clinical Management and the study Coordinating Principal Investigator(s) may be convened. Responsibilities may include oversight of the overall conduct of the study with regard to protocol development, study

progress, subject safety, overall data quality and integrity, and first line review and final decision making of independent medical reviewer recommendations, as well as disseminating any study results through appropriate scientific sessions and publications. Executive Committee members may participate in the review and approval of all requests for data analysis, abstract and manuscript preparation, and submission. As appropriate, the Executive Committee may request participation of WATCHMAN Registry Investigators on the Committee.

## **22. Suspension or Termination**

This study may be terminated at any time. Upon completion or termination, all data must be returned to the sponsor.

## **23. Publication Policy**

The results of this study may be submitted in the form of abstracts to international and/or national congresses and/or in the form of publications to scientific journals. Publication policy will be, at a minimum, dependent on the number of complete patient datasets per site. Boston Scientific is committed to supporting publication of results of Boston Scientific-sponsored clinical research investigations in written or oral publications. Boston Scientific shall do its best to support proposals for sub-analysis and to include as many participating investigators despite the fact that authorship cannot be guaranteed. Therefore clinical investigators are encouraged to identify topics of interest and initiate publications on their own or the pooled data. This will be done in close cooperation with the Sponsor and with the International Study Chairman or/and an Executive committee, if any has been defined. No abstract(s) or article(s) can be submitted for publication without prior authorization from the Sponsor. In accordance with the Corporate Policy on the Conduct of Human Subject Research, Boston Scientific requires disclosure of its involvement as a sponsor or financial supporter in any publication or presentation relating to a Boston Scientific study or its results. In accordance with the Corporate Policy for the Conduct of Human Subject Research, Boston Scientific will submit study results for publication (regardless of study outcome) following the conclusion or termination of the study. Boston Scientific Corporation adheres to the Contributorship Criteria set forth in the Uniform Requirements of the International Committee of Medical Journal Editors (ICMJE; <http://www.icmje.org>). In order to ensure the public disclosure of study results in a timely manner, while maintaining an unbiased presentation of study outcomes, Boston Scientific personnel may assist authors and investigators in publication preparation provided the following guidelines are followed.

- All authorship and contributorship requirements as described above must be followed.
- BSC involvement in the publication preparation and the BSC Publication Policy should be discussed with the Coordinating Principal Investigator(s) and/or Executive/Steering Committee at the onset of the project.

- The First and Senior authors are the primary drivers of decisions regarding publication content, review, approval, and submission.

## Appendix A - Definitions

### *A.1 Stroke/TIA definitions*

#### Broad definitions:

***Transient ischemic attack:*** An episode of acute neurological dysfunction presumed to be caused by transient ischemia, with rapid symptom resolution (usually 1–2 h), resolving completely within 24 hours. Neuroimaging without tissue injury.

***Stroke:*** An episode of acute neurological dysfunction presumed to be caused by ischemia or hemorrhage, persisting  $\geq 24$  hours or until death; preferably with positive neuroimaging study;

#### Stroke diagnostic criteria:

Rapid onset of a focal or global neurological deficit with at least one of the following: change in level of consciousness, hemiplegia, hemiparesis, numbness or sensory loss affecting one side of the body, dysphasia or aphasia, haemianopia, amaurosis fugax, or other neurological signs or symptoms consistent with stroke;

Duration of a focal or global neurological deficit  $\geq 24$  h; OR , 24 h, if therapeutic intervention(s) were performed (e.g. thrombolytic therapy or intracranial angioplasty); OR available neuroimaging documents a new haemorrhage or infarct; OR the neurological deficit results in death

No other readily identifiable non-stroke cause for the clinical presentation (e.g. brain tumour, trauma, infection, hypoglycaemia, peripheral lesion, pharmacological influences)

Confirmation of the diagnosis by at least one of the following:

Neurology or neurosurgical specialist

Neuroimaging procedure (MR or CT scan or cerebral angiography)

Lumbar puncture (i.e. spinal fluid analysis diagnostic of intracranial haemorrhage)

(from From Leon MB, Eur Heart J. 2011 Jan;32(2):205-17)

### *A.2 Classification of Bleeding events*

In response to the need to develop, disseminate, and ultimately adopt standardized bleeding end-point definitions for patients receiving antithrombotic therapy, the Bleeding Academic Research Consortium (BARC) convened in February 2010 at the US Food and Drug Administration (FDA) headquarters in [name]. BARC effort brought together representatives from academic research organizations, the FDA, the National Institutes of Health, and pharmaceutical and cardiovascular device manufacturers and independent physician thought leaders in the field of cardiovascular disease to develop consensus bleeding definitions that would be useful for cardiovascular clinical trials. Application of these definitions is recommended for both clinical trials and registries:

**Type 0:**

No bleeding

**Type 1:**

Bleeding that is not actionable and does not cause the patient to seek unscheduled performance of studies, hospitalization, or treatment by a health-care professional; may include episodes leading to self-discontinuation of medical therapy by the patient without consulting a health-care professional.

**Type 2:**

Any overt, actionable sign of hemorrhage (e.g., more bleeding than would be expected for a clinical circumstance, including bleeding found by imaging alone) that does not fit the criteria for type 3, 4, or 5 but does meet at least one of the following criteria:

1. requiring nonsurgical, medical intervention by a health-care professional,
2. leading to hospitalization or increased level of care, or
3. prompting evaluation

**Type 3:****Type 3a:**

1. Overt bleeding plus hemoglobin drop of 3 to < 5 g/dL\* (provided hemoglobin drop is related to bleed)
2. Any transfusion with overt bleeding

**Type 3b:**

1. Overt bleeding plus hemoglobin drop  $\geq 5$  g/dL\* (provided hemoglobin drop is related to bleed),
2. Cardiac tamponade,
3. Bleeding requiring surgical intervention for control (excluding dental/nasal/skin/haemorrhoid),
4. Bleeding requiring intravenous vasoactive agents

**Type 3c:**

1. Intracranial hemorrhage (does not include microbleeds or hemorrhagic transformation, does include intraspinal),
2. Subcategories confirmed by autopsy or imaging or lumbar puncture,
3. Intraocular bleed compromising vision.

**Type 4:**

1. CABG-related bleeding,
2. Perioperative intracranial bleeding within 48 h,
3. Reoperation after closure of sternotomy for the purpose of controlling bleeding
4. Transfusion of  $\geq 5$  U whole blood or packed red blood cells within a 48-h period,
5. Chest tube output more than or equal to 2L within a 24-h period

**Type 5:**

Fatal bleeding

**Type 5a:**

Probable fatal bleeding; no autopsy or imaging confirmation but clinically suspicious

